## Research plan

The study is planned in a prospective randomized controlled design as illustrated in appendix 1 and 2 and will be carried out in close collaboration with the Department of Urology. The patients will be included and randomized as a part of one of the initial doctors appointments in a consultation room, and they will be encouraged to bring a relative to this consultation. Patients are identified when they have an appointment at Department of Urology, and the researchers will be given information from the clinicians, which means that they will not access the patient journals before enrolling. The patients will be informed about the project from the PhD-student, a physician from the Nuclear Medicine Departments, an Urologist from the cooperating departments or a nurse involved in the project, all with expertise in prostate cancer. They will be offered time to consider enrolment in the trial. The patients will be offered further information and answering of upcoming questions over the telephone after the initial talk. At this time or one of the following days, when they have accepted to be enrolled in the project and signed the written consent, they will be randomized in REDCap, where the randomisation code is kept. The randomization will be stratified according to the patients clinical risk status and pathology of biopsies. The written consents will be collected at the Nuclear Medicine Department, when they meet for their scan and at the earliest the day after the information in Department of Urology. Our study population will comprise men with a newly diagnosed intermediate or high risk (including locally advanced) PCa (1) or with a clinical suspicion of metastases based on other findings. Included patients will be randomized into a control group (A) and an interventional group (B). Group A will be staged by conventional imaging, i.e. CE-CT for N-staging and NaF-PET for M-staging. Group B will be staged by F-PSMA PET/CT for both N- and M-staging. A subset of patients with risk of extracapsular extension considered for radical prostatectomy in group B will also have an F-PSMA-PET/mpMRI-scan for T-staging (evaluation of the tumor). This scan will be performed in continuation of the F-PSMA-PET/CT, i.e. on the same administered dose of F-PSMA. Furthermore, a subgroup of patients in group B will have a blinded NaF-PET-scan for the purpose of performing comparative accuracy analyses.

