Biopsy of suspected metastatic lesions in N- and M-positive patients (suspicion of metastases) as well as lymph node specimen in N- and M-negative patients will be intended as reference standard in both groups as well as a nadir unmeasurably low post-surgery prostate specific antigen blood sample to indicate no residual disease where applicable. Reference standard in the accuracy analysis of F-PSMA PET/mpMRI with regard to T- staging is histopathology on surgical specimen. As the risk of distant metastases increases with increasing PSA-levels, analyses will be performed on both population level as a whole as well as in two PSA-strata with cut-off being PSA=100 ng/ml.

Treatment and subsequent follow-up will be planned on the basis of the results of the scans and according to current guidelines (1, 5).

Follow-up data will be collected from patient journals by the researcher/principal investigator or a delegate, and will consist of clinical information, examination reports, blood test results, information about treatments and pathology reports, all performed in a clinical setup as determined by the clinician. No extra visits, scans or blood test are required except for questionnaires. The patients will be asked to fill in questionnaires (EQ-5D-5L, FACT-P and EPIC 26) concerning quality of life during at baseline and 3, 6, 12, 24, 60, 120 og 236 months after recruitment. The questionnaires will be delivered to the patients e-boks from REDCap automatically at the specific time points. All collected information will be used in this project for analysis of treatment decision, relapse detection, overall survival and quality of life in the two patient groups.

Primary endpoints (Group A vs. B)

1. Treatment strategies and progression-free survival
2. Quality of life measures

Secondary endpoints

1. Overall survival (Group A vs. B)
2.  $^{18}\text{F}$ -PSMA-PET/MR for evaluation of extension of tumor in the prostate gland and surrounding structures compared to histopathology on surgical specimen.
3. Accuracy of  $^{18}\text{F}$ -PSMA-PET/CT compared to NaF-PET/CT for evaluation of bone metastases

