## Feasibility

Patient recruitment will be performed in collaboration with relevant departments of urology in RSD. One or more parallel PhD-projects on the same study population, but nested in the Department of Urology, OUH, is planned, thereby enabling patient recruitment on either of the two departments in close cooperation. It is considered achievable to include the required 448 patients in this setting.

The Department of Nuclear Medicine, OUH, received approval to produce  $^{18}\text{F}$ -PSMA-1007 from the Danish Medicines Agency in 2019.  $^{18}\text{F}$  will routinely be produced on our two cyclotrons, and our well-equipped radiochemistry is trained in the production and labelling of a wide variety of PET-tracers complying with Good Manufacturing Practice (GMP). The tracers will be shipped to the cooperating departments. We currently have five state-of-the-art PET/CT-scanners and a PET/MRI-scanner, and will as such have all the

prerequisites for tracer production and performing the planned scans together with the cooperating Nuclear Medicine Departments.

The PSMA-PET scans performed in OUH will be evaluated and documented as in clinical practice by the applicant and three supervisors as well as a PhD student from another PhD-project - all being Nuclear Medicine specialists along with specialists in radiology, and the same set-up is planned in the cooperating departments. Conventional scans will be evaluated as part of the daily routine at the Departments of Nuclear Medicine (NaF-PET) and Radiology (CE-CT, mpMRI). The SharePoint and RedCap systems will be used for data collection and management in line with the European data protection regulation (GDPR) implemented by May 25 2018. Sharepoint will be used for safe storage of permissions and registrations, and REDCap for patient data.

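### The reference standard cannot find bone metastases that the staging scan misses, so bone sensitivity in group B will be overstated, and the comparison with NaF-PET favours PSMA-PET/CT if NaF-only lesions go unverified

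*Combined protocol and SAP*

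**What the plan says.** The Research plan makes the reference standard depend on the scan result. It intends "Biopsy of suspected metastatic lesions in N- and M-positive patients (suspicion of metastases) as well as lymph node specimen in N- and M-negative patients" in both groups, and adds "a nadir unmeasurably low post-surgery prostate specific antigen blood sample to indicate no residual disease where applicable". T-staging gets its own reference, histopathology of the surgical specimen. Bone gets none.

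Secondary endpoint 3 is the accuracy of PSMA-PET/CT "compared to NaF-PET/CT for evaluation of bone metastases". Planned publication 2 covers N- and M-staging accuracy in group B.

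Group B is staged by "PSMA PET/CT for both N- and M-staging", and "a subgroup of patients in group B will have a blinded NaF-PET-scan for the purpose of performing comparative accuracy analyses". The plan does not say who is blinded, or whether a lesion seen only on NaF-PET counts as suspected. On management it says "Treatment and subsequent follow-up will be planned on the basis of the results of the scans", and on follow-up "No extra visits, scans or blood test are required except for questionnaires". The Feasibility section has conventional scans, NaF-PET among them, read in daily routine.

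The statistical section promises to report missing data and the reasons for data not used. It gives no rule for how men without a bone reference enter sensitivity or specificity.

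**The concern.** Sensitivity needs a count of diseased men that does not depend on the test being assessed. Here a bone metastasis enters the count only if a scan raised suspicion and the lesion was then verified. The two references for scan-negative men cannot add to it: a lymph node specimen does not sample bone, and an unmeasurable PSA only confirms absence of disease in men who were operated on. Men not operated on, or whose PSA stays measurable, have no named reference for bone at all.

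Missed bone disease therefore drops out of the denominator. If only PSMA-PET/CT findings prompt verification in group B, the loss is one-sided: men with PSMA-negative, NaF-positive bone disease are the cases that would count for NaF-PET, and they disappear. What is at stake is the size, and possibly the sign, of the difference reported for secondary endpoint 3 and publication 2.

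**Working it through.** **Inputs.** The documents give no NaF-PET sensitivity and no bone prevalence, so this is an illustration. Assumed: both scans truly 0.85 sensitive for bone; phi, the correlation between the two results in diseased men, at 0, 0.3 and 0.5. The 0.85 is the plan's figure for PSMA-PET/CT and metastases in general. The 128 men are the plan's size for the group B accuracy analyses. Its 30% prevalence is for all metastases, so it is an upper case for bone; 10% is an assumed lower case.

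**Direction.** Suppose no PSMA-negative bone disease is verified. Write sP for true PSMA sensitivity, and u and v for the probability of a positive NaF-PET in diseased men who are PSMA-positive and PSMA-negative.
- Apparent PSMA sensitivity is 1, apparent NaF sensitivity is u, and the apparent difference is 1 − u.
- The true difference is sP(1 − u) − (1 − sP)v.
- Bias = (1 − sP)(1 − u + v). This is never negative, so it always runs toward PSMA.

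**Size.** With equal sensitivities, the share of diseased men positive on one given scan only is b = c = 0.85 × 0.15 × (1 − phi) = 0.1275 / 0.08925 / 0.06375 at phi 0 / 0.3 / 0.5. Let f be the verification rate in PSMA-negative diseased men relative to PSMA-positive ones. Then

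false difference = (b − f·c) / (0.85 + 0.15f).

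| f | phi 0 | phi 0.3 | phi 0.5 |
|---|---|---|---|
| 0 | 15.0 | 10.5 | 7.5 |
| 0.25 | 10.8 | 7.5 | 5.4 |
| 0.5 | 6.9 | 4.8 | 3.4 |
| 0.75 | 3.3 | 2.3 | 1.7 |
| 1 | 0 | 0 | 0 |

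(percentage points; prevalence cancels). For example, f = 0 and phi = 0 gives 0.1275 / 0.85 = 0.150.

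**If lesions on either scan are verified.** Only disease missed by both is lost: 0.15 − b = 0.0225 / 0.06075 / 0.08625. Each apparent sensitivity is 0.85 / 0.9775, 0.85 / 0.93925 and 0.85 / 0.91375, that is 87.0 / 90.5 / 93.0%. The false difference is 0, but both sensitivities are 2.0 / 5.5 / 8.0 points too high.

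**Men involved.** Diseased NaF-only men = 128 × prevalence × c: 4.9 / 3.4 / 2.4 at 30% and 1.6 / 1.1 / 0.8 at 10%, so about 1 to 5.

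**Against sampling error.** With full verification at 30%, there are 128 × 0.30 = 38.4 diseased men. The 95% CI half-width is 1.96 × √(2b / 38.4) = 16.0 / 13.4 / 11.3 points.

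**Bounds from the scans alone.** Assume f = 0, phi 0.3, specificity 0.95 for NaF-PET and 0.98 for PSMA-PET/CT, and independent results in disease-free men. At 30% prevalence:
- NaF-only men are 0.30 × 0.08925 + 0.70 × 0.05 × 0.98 = 0.0268 + 0.0343 = 0.0611 of the total.
- Counting all of them as diseased gives (0.0268 − 0.0611) / (0.255 + 0.0611) = −10.9 points.
- Counting none gives +10.5 points.

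At 15% prevalence the range is −22.8 to +10.5.

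**The case against.** The strongest reply is that verification driven by PSMA alone is not established. The plan does not limit suspected lesions to PSMA findings. The word 'blinded' may mean only that NaF-PET is read without sight of the PSMA result, NaF-PET is read in daily routine, and the Appendix 2 patient flow is a figure not available to this review. A reader might infer that NaF-only lesions are never verified. The documents allow that reading but do not state it, so the bias toward PSMA is conditional. The overstatement of sensitivity is not, because disease missed by both scans is lost on either reading.

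Three other strong readings fail:
- A reader might infer that M-negative men have no reference at all. The PSA clause does cover operated men whose PSA becomes unmeasurable, bone included. It does not repair sensitivity, because it can only confirm negatives.
- A reader might infer that PSMA specificity could not be estimated because only biopsied men would be analysed. No section proposes that analysis, and the PSA clause supplies reference negatives.
- A reader might infer that the 128-patient calculation excludes the bone comparison. The plan counts NaF-PET as the conventional scan for M-staging and ties 128 to the group B accuracy analyses, so its coverage is unclear rather than wrong.

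It is also fair that the practical weight is modest. Only a secondary endpoint and one publication are touched, few men are involved, and at 30% prevalence the worst-case false difference lies below the CI half-width at each phi (15.0 against 16.0, 10.5 against 13.4, 7.5 against 11.3). But a confidence interval does not allow for bias, and more patients would not shrink it.

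**Conclusion.** The concern stands in this form. The stated reference standard does not suit a bone endpoint, because it cannot bring to light bone disease that the staging scan missed. Bone sensitivity in group B will be overstated. If NaF-only lesions are not verified, the difference from NaF-PET is also biased toward PSMA-PET/CT, by 7.5 to 15.0 points with none of the PSMA-negative bone disease verified and 3.4 to 6.9 points with half verified. If lesions on either scan are verified, the false difference between equally sensitive scans vanishes, and 2.0 to 8.0 points of inflation remain in each sensitivity.

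These sizes rest on assumed equal sensitivities of 0.85 and phi from 0 to 0.5. The direction under PSMA-only verification rests on neither. The primary comparisons of group A with group B are not affected. This should be fixed before the accuracy analysis, with medium confidence, because the verification rule is not stated.

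**What to change.** For the group B accuracy study, amend the SAP as follows.

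- Pre-specify one composite bone reference for every man: histology where available, otherwise the imaging, PSA and pathology already collected from the records, judged at a fixed time such as 12 months.
- Apply it to lesions seen on either scan, with NaF-PET unblinded for the analysis only.
- State what blinding of the NaF-PET means and which scan's lesions count as suspected.
- State how men without verification enter sensitivity and specificity.
- Report how many PSMA-negative and how many NaF-only-positive men were verified.
- Add bounds that count unverified NaF-only-positive men first as all diseased, then as none.

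The cost is SAP wording and chart review for about 128 men, with no added biopsy or scan. The composite has limits: it is less certain than histology, still depends partly on PSMA-guided follow-up, may mix missed disease with later progression, and delays publication 2. Since no extra scans are required, some NaF-only men may stay unresolved. The bounds alone may be wide, so the composite has to settle most of these men for the comparison to be informative.

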## Background

PCa is the most frequent cancer form in men in developed countries (3) with approximately 4,500 new cases reported annually in Denmark, 980 of which are based in the Region of Southern Denmark (RSD). The relative 5-year survival is 87% (4). The course of disease ranges from well differentiated tumors localized to the prostate gland itself, being potentially curable, to aggressive, rapidly disseminating variants with poor prognosis despite intensive treatment.

Choice of treatment regimen at primary diagnosis is based on risk stratification, staging of the disease, and general health condition of the patient (1, 5). In intermediate and high risk PCa, further staging procedures besides T-staging (6) is warranted. CE-CT or magnetic resonance (MR) is used for N-staging in cases when pelvic lymph node dissection is avoided during radical prostatectomy or when surgery is refrained from (7), although either modality has a reported sensitivity of approximately 40% (8). M-staging is traditionally obtained from BS, which reflects bone metabolism and has a reported sensitivity as well as specificity of

80% (9). An alternative modality reflecting bone metabolism is the  $^{18}\text{F}$ -sodium fluoride PET/CT (NaF-PET) which has a superior accuracy compared to BS (10, 11). BS has been substituted with NaF-PET in clinical routine at our department, and will as well in this study. Multiparametric MRI (mpMRI) of the pelvis may be performed in high-risk patients for accurate T-staging and thereby planning of resection level (R-staging) before radical prostatectomy.

The treatment regimens for different stages of PCa ranges from observation, radiation therapy, radical prostatectomy and androgen deprivation to intensive chemotherapy and experimental therapeutic regimens (1, 5). The treatment regimens are associated with a specific risk of potential adverse effects, so correct staging is paramount in order to avoid unnecessary treatment complications. Curatively intended surgery or radiation treatment followed by a surveillance program is the initial intervention for patients with localized disease.

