## Sample size and statistical analyses

Assuming that staging intermediate and high risk PCa with  $^{18}\text{F}$ -PSMA PET/CT leads to upstaging in 20%, 398 patients, i.e. 199 patients in each arm, will be necessary to estimate the proportion of upstaged patients with  $^{18}\text{F}$ -PSMA PET/CT with sufficient precision as the expected length of the Wilson-score 95% CI for this proportion will be 11% (simulation study with N=2000 trials). These numbers are sufficient to indicate that the proportion of upstaged patients with  $^{18}\text{F}$ -PSMA PET/CT is statistically significantly larger than 12.9%

under above assumptions (power: 80%; two-sided testing; Type I error: 5%). A total of 448 patients (224 in each arm) are sufficient to indicate a statistically significant difference in progression free survival with assumed hazard rates of 0.35 and 0.5 for 18F-PSMA PET/CT and conventional staging respectively, implying a hazard ratio of 0.7. Estimates are based on a study duration of 4 years, consisting of 3 years accrual time and minimum follow-up period of 1 year before the first data collection, and a loss-to-follow-up of 10% (two-sample comparison of survivor functions; Exponential test; Type I error: 5%). Therefore, **448 patients (224 in each arm)** will be included in the study. For sample size calculation for the accuracy analyses planned in Group B only, we assumed a prevalence of metastases of 30%, sensitivity and specificity of 0.38 and 0.91 for conventional imaging, and 0.85 and 0.98 for PSMA-PET/CT. Then, a sample size of **128 patients** is sufficient to indicate a superior sensitivity for PSMA-PET/CT and a non-inferior specificity for PSMA-PET/CT, with a non-inferiority margin of 0.052, at a significance level of 5% (two-sided) with a power of 80%. We expect 224 patients from OUH, 80 patients from Hospital of Little Belt, 72 patients from Hospital of South West Jutland and 72 patients from Hospital Sønderjylland. Patients from Hospital Sønderjylland will have their scans performed in either Hospital of Little Belt or OUH Odense.

Primary analyses will be done as indicated in the sample size rationale above. Cox proportional hazard regressions will be adjusted for available demographic and clinical baseline variables, and graphical displays will comprise Kaplan-Meier plots including risk tables (i.e. patients at risk in each group).

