## Planned publications

1. Clinical impact on stage migration and treatment strategy when using 18F-PSMA PET/CT compared to conventional imaging in primary staging of PCa (Group A vs B).

2. A prospective comparative accuracy study of 18F-PSMA PET/CT for N- and M-staging compared to conventional imaging in primary PCa (Group B).
3. The added value of PSMA-PET/mpMRI compared to PSMA-PET/CT on T, N, and R-staging (R = resection level) (Subgroup of B).
4. The impact on progression free survival and biochemical relapse when using 18F-PSMA PET/CT compared to conventional imaging in primary staging of PCa (Group A vs. B - planned as a joint publication with PhD student from the Department of Urology).

It is the intention to publish the results no matter if they are positive, negative or inconclusive. The results will be published in [www.clinicaltrialsregister.eu](http://www.clinicaltrialsregister.eu).

Authorship order will be depending on work effort and involvement according to the Vancouver Declaration (IMJCE). No clauses agreed.

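### Scan-negative men who are not operated on have no N-stage reference result, and the plan has no analysis rule for them, so study 2 is open to verification bias

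*Combined protocol and SAP*

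**What the plan says.** The Research plan sets the reference by scan result. For positives it names "Biopsy of suspected metastatic lesions in N- and M-positive patients". For negatives it says that a "lymph node specimen in N- and M-negative patients will be intended as reference standard in both groups", and the sentence goes on: "as well as a nadir unmeasurably low post-surgery prostate specific antigen blood sample to indicate no residual disease where applicable". The same section plans treatment from the scan results and leaves pathology and other follow-up examinations to the treating clinician.

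The Background expects men who will have no node specimen. CT or MR is used for N-staging "in cases when pelvic lymph node dissection is avoided during radical prostatectomy or when surgery is refrained from". It also says: "Curatively intended surgery or radiation treatment followed by a surveillance program is the initial intervention for patients with localized disease".

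N- and M-stage accuracy in group B is the outcome of study 2 (Research plan; second item under Planned publications). The Sample size section takes 128 patients as enough "to indicate a superior sensitivity for PSMA-PET/CT and a non-inferior specificity for PSMA-PET/CT". It makes no allowance for men without a reference result. On missing data the statistical section says only that it will be reported.

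**The concern.** A man with a negative scan gets an N-stage reference only through surgery, by node dissection or by a PSA nadir too low to measure. A man with a positive scan is meant to get one by biopsy, which does not require surgery. Two groups of scan-negative men are left without a reference: those not operated on, and those operated on without dissection whose PSA stays measurable. By the Background's own account, men without dissection or surgery are the ones in whom imaging is relied on for N-staging.

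Whether a man is verified thus depends on the result of the test under study. If unverified men are dropped, missed nodal disease drops out with them and PSMA sensitivity rises. True negatives are also lost while false positives stay, so specificity falls and the non-inferiority test has fewer men. The PSA nadir does not repair the sensitivity bias, because it can confirm absence of disease but cannot reveal a missed node.

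**Working it through.** **Inputs from the Sample size section.** 128 men; prevalence 0.30; sensitivity 0.85 (PSMA) and 0.38 (conventional); specificity 0.98 and 0.91; margin 0.052; two-sided 5%; power 80%.

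**Assumptions not in the documents.** The 30% prevalence of metastases, and the accuracy figures, apply to N-stage. The errors of the two scans are independent given disease state. vp and vn are the shares of PSMA-positive and PSMA-negative men with a reference result; the documents give neither, so they are varied.

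**The plan's 128.** No method is named and I could not reproduce the figure exactly. For specificity with independent errors, the discordant share is 0.98×0.09 + 0.02×0.91 = 0.1064 and the true difference is 0.07. The non-diseased men needed are (1.96+0.84)² × (0.1064 − 0.07²) / (0.07+0.052)² ≈ 54, or 54/0.70 ≈ 77 in total. Over other methods and degrees of discordance, specificity needs 49–79 patients and sensitivity 47–96. So 128 is ample if every man has a reference result.

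**Expected counts in 128 men.** Diseased 38.4, non-diseased 89.6. PSMA-positive: 0.85×38.4 + 0.02×89.6 = 32.64 + 1.79 = 34.4. PSMA-negative: 5.76 diseased + 87.81 non-diseased = 93.6.

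**Verified men only.**
- Observed sensitivity = 0.85·vp / (0.85·vp + 0.15·vn)
- Observed specificity = 0.98·vn / (0.98·vn + 0.02·vp)
- Example, vp = 1, vn = 0.4: 0.85/(0.85+0.06) = 0.934; 0.392/(0.392+0.02) = 0.951

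Power for non-inferior specificity was simulated (20,000 trials per setting, paired Wald interval):

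| vp / vn | Men scored | PSMA sensitivity | PSMA specificity | Power |
|---|---|---|---|---|
| 1 / 1 | 128 | 0.85 | 0.98 | 0.97 |
| 1 / 0.8 | 109 | 0.88 | 0.975 | 0.90 |
| 1 / 0.6 | 91 | 0.90 | 0.967 | 0.71 |
| 1 / 0.4 | 72 | 0.93 | 0.951 | 0.41 |
| 0.6 / 0.6 | 77 | 0.85 | 0.98 | 0.86 |
| 0.5 / 0.8 | 92 | 0.78 | 0.987 | 0.98 |

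Conventional sensitivity stays at 0.38 in these settings, so with vp = 1 the gap in favour of PSMA-PET/CT widens. Power for superior sensitivity stays at 0.99 or above in the rows with vp = 1. If a positive result on either scan led to verification, PSMA sensitivity would be 0.883 and 0.900 at vn = 0.6 and 0.4. That is a smaller bias in the same direction.

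**Crediting the PSA nadir.** Suppose a further 20% of PSMA-negative men are operated on without dissection and 90% of the true negatives among them reach the nadir. With vp = 1, specificity is 0.975 at vn = 0.6 and 0.966 at vn = 0.4, and power is 0.88 and 0.69. Sensitivity stays at 0.90 and 0.93.

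**Does a correction work?** Take vp = 1, vn = 0.4. Verified PSMA-negatives are 0.4×5.76 = 2.30 diseased and 0.4×87.81 = 35.12 non-diseased, a diseased share of 2.30/37.43 = 0.0616. Applied to all 93.6 PSMA-negatives this returns 5.76 missed cases, and sensitivity is 32.64/(32.64+5.76) = 0.85. Specificity returns to 0.98 in the same way.

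**The case against.** Four objections carry weight.

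- **The PSA nadir is a second reference.** A reader might infer that every man without node dissection is unscorable. The text does not support that: a man operated on without dissection can be scored negative if his PSA becomes too low to measure. As shown above, this restores part of the specificity power but none of the sensitivity bias.
- **Bias is not certain.** A reader might infer that N-stage accuracy is necessarily biased. Biopsy of positives is only intended, and pathology is left to the clinician. Equal verification gives no bias of this kind, and verifying positives less often reverses it. Still, the plan offers positives and negatives different routes to a reference, so equality would be a coincidence.
- **128 may be enough.** A reader might infer that 128 men cannot deliver the stated power. With all positives verified, power is 0.81 at vn = 0.7 and higher above that. The section also does not say that only 128 men will be compared. Group B has 224, and the dose list under Ethical aspects includes contrast-enhanced CT in the PSMA-PET/CT, so an N-stage comparison might use all of them. Without the PSA nadir, 224 men give power of about 0.90 at vn = 0.6, just under 0.80 at 0.5 and 0.59 at 0.4. More men restore power but do not remove bias.
- **Scope.** N-stage accuracy is a study 2 outcome and is not among the listed primary or secondary endpoints. The randomised comparisons are unaffected.

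**Conclusion.** The gap is real. The plan gives no N-stage reference for scan-negative men who are not operated on, or for men operated on without dissection whose PSA stays measurable, and it has no method for analysing them.

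If positives are verified more often than negatives and only verified men are analysed, PSMA sensitivity is expected to be overstated by about 3 to 8 points (0.88 to 0.93 against 0.85) for vn from 0.8 down to 0.4. Specificity is expected to be understated by about 0.5 to 3 points (0.975 to 0.951 against 0.98). Power for the specificity test stays above the planned 80% at vn = 0.8. It falls to 0.71 and 0.41 at 0.6 and 0.4, or 0.88 and 0.69 with the assumed credit for the PSA nadir.

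These sizes rest on the assumed verified shares, independent errors, and the plan's 30% taken as N-stage prevalence. The documents do not show which case applies. The point should be settled before study 2 is analysed.

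**What to change.** For the N-stage analysis of study 2:

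1. Keep unverified men in the analysis through a verification-bias correction: Begg-Greenes, or multiple imputation using both scan results, PSA, Gleason score and clinical T stage.
2. In that correction, count histology as verification. Do not count men scored only by the PSA nadir as ordinary verified men, because they are selected for being disease-free. In the vn = 0.4 example, the nadir adds 0.2×0.9×87.81 = 15.8 negatives. The diseased share becomes 2.30/53.2 = 0.043, and the corrected sensitivity is 32.64/(32.64 + 0.043×93.6) ≈ 0.89 rather than 0.85.
3. Report the verified-only (histology) analysis as a sensitivity analysis. Optionally add one that assigns node status from the journal follow-up already collected. That should not be the main analysis: PSA course is not node-specific, is altered by treatment, and the journals reflect scan-driven care.
4. In the Sample size section, state that 128 means men with a reference result, or restate the specificity power for the expected verified number.

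This needs no extra scans, biopsies or patients. The costs are some analysis work, reliance on a missing-at-random assumption, wider intervals, and possibly a less favourable stated power.
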